Appendix 3 Handling and Shipment of Bioanalytical Samples

All tubes must be labeled using the central laboratory's bar code labels provided with the sample collection kits. The central laboratory's requisition form must be completely filled out in regards to all the sample information. In addition, the subject ID number and date of collection must be hand-written on the sample tube. It is important to note the exact time of the blood collection on the eCRF.

Each specimen must be labeled using a waterproof pen. A label suitable for the storage conditions must contain the subject ID number and date of collection, must correspond to the requisition form, and must be firmly attached. The requisition form must contain the name, address, and telephone number of the contact person from the trial site.

Plasma Samples for Tolvaptan

Blood (1 mL) will be collected into plastic Vacutainer tubes containing lithium heparin anticoagulant. The tubes should be gently inverted 3 to 4 times and then centrifuged at 2,000 to 3,000 rpm for at least 10 to 15 minutes at 4°C. The rpm should be kept at a constant setting throughout the trial. Plasma should be stored at -20°C or on dry ice. Samples should be shipped monthly.

Shipment of Plasma

Plasma samples must be neatly packed in the kits provided by the central laboratory and restrained in a Styrofoam container that is completely filled with dry ice to avoid air spaces that allow evaporation of the dry ice. The Styrofoam container should be sealed with tape and placed in a cardboard box. The central laboratory must be alerted of sample shipment. Packages must not be shipped on Thursday, Fridays, Saturdays, or any day prior to a holiday without the expressed consent of OPDC or the central laboratory. Shipments from clinical trial sites will be via an overnight carrier to the central laboratory (Clinical Laboratory Supplies, Covance Central).

Appendix 4 Tanner Staging
Classification of Sex Maturity Stages in Girls

Stage	Pubic Hair	Breasts
1	Preadolescent	Preadolescent
2	Sparse, lightly pigmented, straight, medial border of labia	Breast and papilla elevated as small mound; areolar diameter increased
3	Darker, beginning to curl, increased amount	Breast and areola enlarged, no contour separation
4	Coarse, curly, abundant but amount less than adult	Areola and papilla form secondary mound
5	Adult feminine triangle, spread to medial surface of thighs	Mature; nipple projects, areola part of the general breast contour

Classification of Sex Maturity Stages in Boys

Stage	Pubic Hair	Penis	Testes
1	Preadolescent	Preadolescent	Preadolescent
2	Scanty, long, slightly pigmented	Slight enlargement	Enlarged scrotum, pink texture altered
3	Darker, starts to curl, small amount	Longer	Larger
4	Resembles adult type but less in quantity; coarse, curly	Larger; glans and breadth increase in size	Larger, scrotum dark
5	Adult distribution, spread to medial surface of thighs	Adult size	Adult size

Appendix 5 Optional Tolvaptan Treatment Component: Eligibility Criteria

Subjects will be eligible for tolvaptan treatment if they meet the criteria outlined in the table below.

Eligibility Criteria for Optional Tolvaptan Treatment	
1.	Male or female subjects ≥ 4 years of age (or per local Health Authority age restrictions) and ≥ 10 kg
2.	The subject must have been off treatment with the investigational medicinal product (IMP) for at least 7 days following the end of treatment in the previous tolvaptan trial for hyponatremia (euvolemic or hypervolemic)
3.	Persistent dilutional (euvolemic or hypervolemic) hyponatremia defined as being documented as present for at least 48 hours, evidenced by at least 2 serum sodium assessments < 130 mEq/L (mmol/L) drawn at least 12 hours apart (these values can be documented using historical values previously obtained per standard of care); a third (STAT) serum sodium assessment < 130 mEq/L (mmol/L), which will serve as the baseline value for efficacy endpoints, is to be obtained within 2 to 4 hours prior to the first dose of tolvaptan
4.	Ability to swallow tablets
5.	Ability to maintain adequate fluid intake whether orally or via IV support with adequate monitoring
6.	Ability to comply with all requirements of the trial
7.	Trial-specific written informed consent/assent obtained from a parent/guardian or legally acceptable representative, as applicable per age of subject or local laws, prior to the initiation of any protocol-required procedures. In addition, the subject as required by local laws must provide informed assent at the pretreatment baseline for this trial and must be able to understand that he or she can withdraw from the trial at any time. All informed consent/assent procedures must be in accordance with the trial center's IRB/IEC and local regulatory requirements
8.	Ability to commit to remain fully abstinent (periodic abstinence [eg, calendar, ovulation, symptothermal, post-ovulation methods] or withdrawal are not acceptable methods of contraception) or practice double-barrier birth control during the trial and for 30 days following the last dose of tolvaptan for sexually active females of childbearing potential

Subjects will be ineligible for tolvaptan treatment if they meet any of the following criteria:

Ineligibility Criteria for Tolvaptan Treatment	
1.	Has evidence of hypovolemia or intravascular volume depletion (eg, hypotension, clinical evidence of volume depletion, response to saline challenge); if the subject has systolic blood pressure or heart rate outside of the normal range for that age volume status should be specifically clinically assessed to rule out volume depletion.
2.	Has serum sodium < 120 mEq/L (mmol/L), with or without associated neurologic impairment (ie, symptoms such as apathy, confusion, or seizures)
3.	Use of potent CYP3A4 inhibitors in subjects ≤ 50 kg or moderate CYP3A4 inhibitors in subjects < 20 kg
4.	Lacks free access to water (inability to respond to thirst) or without ICU-level fluid monitoring and management
5.	Has a history or current diagnosis of nephrotic syndrome
6.	Has transient hyponatremia likely to resolve (eg, head trauma or post-operative state)
7.	Has hyperkalemia defined as serum potassium above the ULN for the appropriate pediatric age range

Ineligibility Criteria for Tolvaptan Treatment	
8.	Has eGFR < 30 mL/min/1.73 m ² calculated by the following equation: eGFR (mL/min/1.73 m ²) = 0.413 × height (cm)/serum creatinine (mg/dL)
9.	Has acute kidney injury defined as: 
 • Increase in serum creatinine by ≥ 0.3 mg/dL (≥ 26.5 μmol/L) within 48 hours; or • Increase in serum creatinine to ≥ 1.5 times baseline, which is known or presumed to have occurred within the prior 7 days; or • Urine volume < 0.5 mL/kg/h for 6 hours
10.	Has severe or acute neurological symptoms requiring other intervention (eg, hyperemesis, obtundation, seizures)
11.	Has had treatment for hyponatremia with: 
 • Hypertonic saline (including normal saline challenge) within 8 hours of qualifying serum sodium assessments; • Urea, lithium, demeclocycline, conivaptan, or tolvaptan within 4 days of qualifying serum sodium assessments; • Other treatment for the purpose of increasing serum sodium concurrent with dosing of trial medication
12.	Has anuria or urinary outflow obstruction, unless the subject is, or can be, catheterized during the trial
13.	Has a history of drug or medication abuse within 3 months prior to the pretreatment visit or current alcohol abuse
14.	Has a history of hypersensitivity and/or idiosyncratic reaction to benzazepine or benzazepine derivatives (such as benazepril)
15.	Has psychogenic polydipsia (subjects with other psychiatric illness may be included per medical monitor approval)
16.	Has uncontrolled diabetes mellitus, defined as fasting glucose > 300 mg/dL (16.7 mEq/L [mmol/L])
17.	Has screening liver function values > 3 × ULN.
18.	Patient who has cirrhosis and meets any of the following conditions: a major GI bleed within the past 6 months, evidence of active bleeding (eg, epistaxis, petechiae/purpura, hematuria, or hematochezia), platelet count < 50,000/μL, or use of concomitant medications known to increase bleeding risk
19.	Has hyponatremia due to the result of any medication that can safely be withdrawn (eg, thiazide diuretics)
20.	Has hyponatremia (eg, hyponatremia in the setting of adrenal insufficiency, untreated hypothyroidism, or hypotonic fluid administration) that is most appropriately corrected by alternative therapies
21.	Is currently pregnant or breastfeeding
22.	Has any medical condition that, in the opinion of the investigator, could interfere with evaluation of the trial objectives or safety of the subjects
23.	Is deemed unsuitable for trial participation in the opinion of the investigator
24.	Participation in an investigational drug trial (other than a previous tolvaptan hyponatremia trial) within the past 30 days, without prior approval from the medical monitor
25.	Subjects < 4 years of age (or per local Health Authority age restrictions), weight < 10 kg, or who are unable to swallow tablets

AKI = acute kidney injury; eGFR = estimated glomerular filtration rate; GI = gastrointestinal;
ICU = intensive care unit; IRE = Immediately Reportable Event; ULN = upper limit of normal

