3.1.2 Optional Tolvaptan Treatment Component

Subjects enrolled in the 6-month core safety follow-up component may be eligible to receive optional tolvaptan treatment for their hyponatremia. Eligibility criteria for optional tolvaptan treatment are outlined in [Appendix 5](#). Eligibility for optional tolvaptan treatment must be determined at the pre-treatment baseline visit (Day -4 to Day -1) of each dosing cycle. Eligible subjects can be treated at any time with optional tolvaptan during the 6-month core safety follow-up component. Optional tolvaptan treatment duration will be case-specific; it can be short-term or long-term, and consist of 1 or more treatment cycles. When a cycle with optional tolvaptan treatment is completed, including the Follow-up Phase visits, subjects will continue in the core safety component to complete the remainder of visits until Month 6. Within this trial, tolvaptan treatment will not extend beyond the 6-month core safety trial period. If the subject completes the 6-month core safety component while on optional tolvaptan treatment, the subject will complete the Month 6 core safety component visit, terminate treatment, and immediately enter the Follow-up Phase.

If a subject simultaneously participates in both core safety and optional tolvaptan treatment components, the visit days will be calculated between both components to ensure the assessments can be overlapped, where applicable.

3.1.2.1 Treatment Interruption on Day 30

Thirty days after the start of optional tolvaptan treatment, subjects will interrupt treatment for up to 2 doses (Days 31-32). The need for continuing treatment after this tolvaptan interruption will be assessed at minimum once daily (or more as needed) during this time.

Subjects who are expected to receive tolvaptan for greater than 30 days duration should demonstrate the need for continued treatment by discontinuing tolvaptan for up to 2 consecutive doses while undergoing close monitoring of serum sodium levels.

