3.7.3.2 Optional Tolvaptan Treatment Component

Subjects may become eligible for tolvaptan treatment at any time while participating in the 6-month core safety follow-up component if they have dilutional (euvolemic or hypervolemic) hyponatremia (serum sodium < 130 mEq/L [mmol/L]). The investigator is required to call the medical monitor to discuss the appropriateness of tolvaptan treatment for subjects who discontinued from the previous trial of titrated oral IMP early or demonstrated a lack of response to tolvaptan, but have a demonstrated clinical need for tolvaptan. Subjects participating in the optional tolvaptan treatment component will concurrently maintain visit assessments in the core safety follow up component up to and including the Month 6 final visit. Core safety follow-up assessments can be scheduled per the defined windows and at the convenience of the subject's optional tolvaptan treatment visit schedule.

Since hyponatremia in this patient population can often be transient and/or may be secondary to hypovolemic states, potential subjects will be screened for hyponatremic histories as well as clinically evaluated to exclude such cases from the optional tolvaptan treatment component of the trial. To be eligible for the optional tolvaptan treatment component of this protocol, subjects must have persistent dilutional (euvolemic or hypervolemic) hyponatremia, defined as serum sodium assessments < 130 mEq/L (mmol/L) that are documented for at least 48 hours after the final dose of IMP in the previous trial and prior to the planned initiation of tolvaptan titration in this trial. These values can be documented using historical values previously obtained per standard of care. A third (immediate [STAT]) serum sodium assessment < 130 mEq/L (mmol/L), which will serve as the final treatment qualification, management strategy, and baseline

value for efficacy endpoints, is to be obtained within 2 to 4 hours prior to the first dose of tolvaptan. Additional qualification assessments will be performed per etiology of hyponatremia ([Section 3.3.2](#)).

The procedures to be performed at the required visits for subjects in need of tolvaptan treatment and for each tolvaptan treatment cycle are summarized in this section.

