3.7.3.2.1 Pretreatment Baseline Visit

The following procedures will be performed during the pretreatment baseline visit (Days -4 to -1) to ensure the subject qualifies for each tolvaptan treatment cycle:

- 1) Eligibility criteria (see [Appendix 5](#)) will be reviewed.
- 2) A clinical status assessment including a full neurological examination will be performed. If the subject has any positive findings on the clinical status assessment at the second or subsequent pretreatment baseline visits, a full neurological examination can be performed per investigator judgment.
- 3) Vital signs (blood pressure, heart rate, respiratory rate, and temperature) will be assessed at each visit after the subject has been supine for ≥ 3 minutes. Vital signs should be performed prior to the blood draws.
- 4) A full physical examination will be performed if it overlaps with the same assessment at the core safety baseline visit. Otherwise, a directed physical examination will be performed. Physical examination should include a fontanelle assessment as age appropriate.
- 5) Body height will be measured.
- 6) Body weight will be measured.
- 7) Growth percentile will be calculated.
- 8) A blood sample for ALT, AST, BT and creatinine will be collected.
- 9) A urine or serum pregnancy test will be performed on female subjects ≥ 12 years of age and female subjects < 12 years of age if menstruation has started.
- 10) Within 48 hours prior to tolvaptan administration, 2 samples for serum sodium testing will be collected at least 12 hours apart.
- 11) Quality of Life assessment will be performed, as appropriate by age and where available.
- 12) Concomitant medications will be recorded.
- 13) Adverse events will be assessed.

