3.7.3.2.2 Titration Phase

A subject who requires tolvaptan treatment can be treated for as many cycles as deemed necessary by the investigator within the 6 month trial period. The duration of treatment cycles may vary per the investigator's assessment of clinical need. Regardless of the number of treatment cycles and the duration of tolvaptan treatment in each cycle, optional tolvaptan treatment cycles will consist of a titration phase, a maintenance phase, and a follow-up phase. The schedule of assessments for the optional tolvaptan treatment component is shown in [Table 3.7.2-1](#).

The first dose of tolvaptan will be administered upon successful completion of all pretreatment baseline procedures. Subjects will enter a titration phase and follow the titration schedule outlined in [Section 3.2.1.2](#). Subjects will be required to be in a hospital setting during initiation and titration of tolvaptan.

During the Titration Phase on Day 1 up to Day 4 of treatment, in addition to serum sodium samples obtained for treatment qualification and efficacy endpoints, supplemental samples for the purposes of safety assessment will be obtained using a point of care (POC) sodium assessment unit, where available, at 4 to 6 (+0.25) hours postdose and at 18 (\pm 1) hours postdose. A POC assessment unit is preferred; however, regular blood draws may be used (especially if they can be combined with standard of care labs). A schedule of blood samples required for serum sodium assessments can be found in [Table 3.7.4.1.2-1](#).

3.7.3.2.2.1 Day 1

All titration of tolvaptan will be done in a hospital setting. Please see [Section 3.2.1](#) for details on titration and dosing.

The following procedures will be performed on Day 1:

- 1) Vital signs (blood pressure, heart rate, respiratory rate, and temperature) will be assessed after the subject has been supine for \geq 3 minutes. Vital signs should be assessed prior to blood draws.
- 2) A blood sample for STAT serum sodium testing will be collected within 2 to 4 hours prior to the first dose. Results need to be reviewed prior to dosing to confirm continued treatment eligibility of the subject.

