3.7.4.1.2 Supplemental Sodium Samples for Safety

In addition to serum sodium samples obtained for treatment qualification and efficacy endpoints, supplemental samples for the purposes of safety assessment only will be obtained using a POC sodium assessment unit, where available. A POC assessment unit is preferred; however, regular blood draws may be used (especially if they can be combined with standard of care labs). The supplemental sodium samples for safety assessments are found in [Table 3.7.4.1.2-1](#).

Table 3.7.4.1.2-1 Serum Sodium Assessments During the Optional Tolvaptan Component				
Treatment Cycle	Phase	Day	Blood Draws for Serum Sodium	
			Efficacy	Supplemental Safety
Month 1	Pretreatment baseline	-4 to -1	Within 48 hours prior to tolvaptan administration, 2 blood samples, 12 hours apart	-
	Titration	1	2 to 4 hours prior to the first dose	-
			8 (-1 to + 0.25) hours postdose	4 to 6 (+ 0.25) hours postdose
		-	18 (± 1) hours postdose	
		2, 3, and 4	24 (± 4) hours post previous dose (trough)	6 (-1 to +0.25) hours and 18 (±1) hours postdose
Posttitration treatment	7, 14 and 21	24 (± 4) hours post previous dose	-	
Day 30 interruption		30	24 (± 4) hours post previous dose	-
		31	24 (± 4) hours post previous dose	
		32	48 (± 4) hours post previous dose	-
		33	72 (± 4) hours post previous dose	-
		34	24 (± 4) hours post previous dose	-
Month 2	Treatment	Every 14 (± 2) days	24 (± 4) hours post previous dose	-
Months 3, 4 and 5	Treatment (Maintenance)	Every month (± 2 days)	24 (± 4) hours post previous dose	-
Month 6/ET	Trial termination	-	Month 6 or trial termination	-
Follow-up	Follow-up	-	24 (± 4) hours post-previous dose	-
		-	7 (±1) days post last dose	-

Additional details can be found in [Section 3.7.3.2](#).

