Appendix 6 Optional Tolvaptan Treatment Component: Laboratory Assessment Schedule

Frequency of Recurring Laboratory Assessments			
Treatment Phase	Serum Sodium	LFTs (ALT, AST, BT) and creatinine	PK^a
Pretreatment Baseline doses	Day -1 to Day -4: assessments \leq 130 mEqL (mmol/L) \geq 12 hours apart	Required at baseline if not done within the previous month	
Month 1: Titration ^b	Once daily efficacy assessment and additional safety assessments 4 to 6 hours and 18 hours postdose		
Month 1: Post-titration ^c	Once weekly	Once monthly	
Month 2: Post-titration (steady dose)	Every 2 weeks	Once monthly	Once post 8 weeks of continuous treatment
Month 3+ post-titration (steady dose): Maintenance (Months 3, 4, and 5)	Once monthly	Once monthly ^{d,e}	
Month 6	24 (\pm 4) hours postdose	Once	
Post-last dose Follow-up each cycle	24 (\pm 4) hours and 7 (\pm 1) days		

^a Once post 8 weeks for every new cycle of treatment

^b Day 1 up to Day 4

^c Days 7, 14, and 21

^d AST, ALT, and BT will be assessed if more than 1 month has elapsed since LFTs were performed

^e See Section 3.7.5.3.1 for more information and [Section 5.4](#) for detailed instructions on follow-up of subjects with elevations in AST, ALT, or BT that are $\geq 2 \times$ ULN or levels that increase $\geq 2 \times$ from baseline.

NA = Not applicable.

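### Criterion 3 requires hyponatremia documented for at least 48 hours, but the evidence it names and the scheduled sodium draws do not deliver that duration

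*Protocol*

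**What the plan says.** **The rule.** Protocol Appendix 5, eligibility criterion 3, defines persistent dilutional hyponatremia as "documented as present for at least 48 hours, evidenced by at least 2 serum sodium assessments" below 130 mEq/L, the two being drawn at least 12 hours apart. A third, STAT value below 130 follows, 2 to 4 hours before the first dose. Historical standard-of-care values may be used but are not required. Section 3.7.3.2 repeats the duration, asking for values below 130 "that are documented for at least 48 hours after the final dose of IMP". The same sentence closes the period at a point "prior to the planned initiation of tolvaptan titration in this trial".

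**The schedule.** Section 3.7.3.2.1, step 10: "Within 48 hours prior to tolvaptan administration, 2 samples for serum sodium testing will be collected at least 12 hours apart". Table 3.7.4.1.2-1 agrees: "Within 48 hours prior to tolvaptan administration, 2 blood samples, 12 hours apart". Section 3.7.3.2.2.1 puts the third draw on Day 1: "A blood sample for STAT serum sodium testing will be collected within 2 to 4 hours prior to the first dose". Appendix 6 has "Day -1 to Day -4: assessments" at 130 or less, at least 12 hours apart, with no 48-hour span.

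**Frequency.** Under Section 3.1.2, eligibility "must be determined at the pre-treatment baseline visit (Day -4 to Day -1) of each dosing cycle".

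**The concern.** One sentence of criterion 3 sets a duration and then names evidence that need not show it. The schedule adds to the difficulty. In the criterion, 48 hours is the least time for which low sodium must be documented; in step 10 and the table, it is the greatest age that a scheduled draw may have. The two meet only for a draw at exactly 48 hours. No section says outright that one value must be at least 48 hours old.

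The 48-hour rule is the plan's only numeric test of persistence. Section 3.7.3.2 itself notes that hyponatremia in these children is often transient, and Section 5.3.1.1 warns that overly rapid correction can lead to osmotic demyelination. A site that leaned on the named evidence and the scheduled draws could treat a child who does not meet the definition, and the question returns at every cycle.

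**Working it through.** **Inputs**
- Required duration: at least 48 h (Appendix 5, criterion 3; Section 3.7.3.2).
- Spacing of the two values: at least 12 h (criterion 3; Section 3.7.3.2.1; Table 3.7.4.1.2-1).
- Both on-study draws no more than 48 h before dosing (Section 3.7.3.2.1, step 10; the table).
- STAT draw 2 to 4 h before the first dose, on Day 1 (Section 3.7.3.2.2.1; the table).
- The two earlier draws belong to Days -4 to -1 (Section 3.7.3.2.1; the table).
- Dosing preferably in the morning (Sections 3.2.1.1 and 3.2.1.2).

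**Assumptions.** The documents give no clock time. I take an 08:00 first dose, calendar days, no Day 0, and both earlier draws before the STAT draw.

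**Notation.** In hours before the first dose, let the first draw be at *a*, the second at *b* and the STAT draw at *s*. Then *a* − *b* ≥ 12, *b* ≥ *s* and 2 ≤ *s* ≤ 4; the scheduled draws add *a* ≤ 48. The documented span is *a* to the first dose and *a* − *s* to the STAT draw. Criterion 3 does not say where its 48 h ends; Section 3.7.3.2 points to the start of titration, so the first dose is the better-supported endpoint.

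**Longest span from scheduled draws.** Set *a* = 48. To the first dose: 48 h. To the STAT draw: 48 − 2 = 46 h, or 48 − 4 = 44 h.

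**Shortest span from the evidence named in criterion 3, taken alone.** Set *b* = *s*, so *a* = *s* + 12. To the STAT draw: 12 h. To the first dose: 14 h with *s* = 2, or 16 h with *s* = 4.

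**Shortest span from scheduled draws with a morning dose.** The latest Day -1 draw is just before midnight, 8 h before an 08:00 dose, so *b* = 8 and *a* = 8 + 12 = 20. To the first dose: 20 h. To the STAT draw: 20 − 2 = 18 h, or 20 − 4 = 16 h.

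| Case | To first dose | To STAT draw | Share of 48 h |
|---|---|---|---|
| Scheduled draws, longest | 48 h | 46 h | 100% / 96% |
| Scheduled draws, shortest, 08:00 dose | 20 h | 16 to 18 h | 42% / 33 to 38% |
| Named evidence alone, shortest | 14 h | 12 h | 29% / 25% |

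Shortfall to the first dose: 48 − 20 = 28 h with the morning dose, and 48 − 14 = 34 h at the theoretical extreme.

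**Can a repaired rule be met?** With no Day 0, the same clock time on Day -4 is about 96 h before the Day 1 dose, so a value at or before −48 h fits the baseline window. Draws at −50 h and −24 h with a STAT draw at −3 h work: 50 ≥ 48; 24 ≤ 48 and 50 − 24 = 26 ≥ 12; 3 lies between 2 and 4.

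**The case against.** **The 48-hour definition binds as it stands.** The phrase about two values sets a minimum number and spacing and does not replace the duration. A reader might infer that a child with 12 to 14 hours of documentation qualifies. The documents do not support that: such a child fails criterion 3 and Section 3.7.3.2, and treating that child would breach the rule. This part of the objection stands. It does not remove the mismatch, because the sentence offers evidence as proof of a duration that the evidence need not show.

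**The schedule may serve recency only.** On this view an older historical value shows duration, the two draws show that sodium is still low, and the STAT value gives baseline. That is a sensible structure, but the text never states it: historical values are permitted, not required, and nothing assigns them this task.

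**The shortest figures are not realistic for scheduled draws.** A reader might also infer that the scheduled draws can span only 12 to 14 hours. That puts the second draw right beside the STAT draw, although one belongs to Days -4 to -1 and the other to Day 1. It would need a first dose at about 02:00, against the stated preference for mornings. About 20 hours is the fairer minimum.

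**Other safeguards exist.** Section 3.7.3.2 requires history screening and clinical evaluation to exclude transient cases. Section 3.3.2 excludes acute or self-resolving cases and bars treatment if any pretreatment baseline value is 130 or more. Appendix 5, ineligibility item 6, excludes transient hyponatremia. These reduce the risk, but none sets a time, and the bar at 130 works only if such a value was drawn. Sections 9.1 and 9.2 require source records and documented criteria review, so the span used could be checked afterwards.

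**Conclusion.** The point holds as a mismatch inside an eligibility rule. The plan requires at least 48 hours, the named evidence can show as little as 12, and the scheduled draws alone give between about 20 and 48 hours to the first dose, reaching 48 only at the boundary and never exceeding 46 to the STAT draw. The 20-hour figure rests on the 08:00 dose and calendar-day assumptions; the 46- and 48-hour limits do not.

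A reader might infer that children were treated on thin evidence or that efficacy results are compromised. Neither follows: SAP Section 5.1 reports that no subject received optional tolvaptan, so no child and no analysis was affected. The wording should still be corrected, because it is a patient-safety rule and the text may be reused.

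A smaller inconsistency has no bearing on duration: Appendix 6 accepts 130 or less, while Section 3.3.2 and criterion 3 require less than 130.

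**What to change.** - In criterion 3, state that the earliest qualifying value below 130, historical or on-study, must be at least 48 hours before the first dose. This also settles where the 48 hours ends.
- Keep at least one further value below 130 within 48 hours of dosing and at least 12 hours after the first, and keep the STAT value, so that recency is not lost.
- Reword step 10 of Section 3.7.3.2.1 and Table 3.7.4.1.2-1 to match.
- Leave the bar on values of 130 or more as it is in Section 3.3.2, confined to the pretreatment baseline period.
- Correct Appendix 6 from 130 or less to below 130.

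**Cost.** These are wording changes and one symbol. Compared with a site relying on the scheduled draws alone, a child without an eligible older value may wait about 28 hours longer with a morning dose (34 at the theoretical extreme) and may need one more blood draw. A child with an eligible older value is not delayed. At reinitiation that help may be missing: Appendix 5, ineligibility item 11, rules out qualifying values within 4 days of tolvaptan, so a recent standard-of-care value may not count. An eCRF field for the time of the earliest value is optional, since source records are already required.
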